2.2. Study Objective(s) and Endpoint(s)

Objectives	Endpoints
Primary Objectives	Primary Endpoints

 To demonstrate non-inferiority of GSK1278863 to epoetin beta pegol based on hemoglobin (Hgb) in ND subjects 	
 Mean Hgb during the primary efficacy evaluation period (Weeks 40 to 52)
Principal Secondary Objectives	Principal Secondary Endpoints

 To demonstrate superiority of GSK1278863 to epoetin beta pegol in terms of achievement/maintenance of target Hgb in ND subjects 	
 Number (%) of subjects with mean Hgb in the target range (11.0-13.0 g/dL) during the primary efficacy evaluation period (Weeks 40 to 52)
Other Secondary Objectives	Other Secondary Endpoints

 To evaluate the appropriateness of the starting dose of GSK1278863 in ND subjects using epoetin beta pegol as control To evaluate the appropriateness of the starting dose of GSK1278863 in PD subjects 	
 Change in Hgb from baseline to Week 4 (Hgb increase rate) Number (%) of subjects by Hgb change category in Hgb from baseline to Week 4

 To evaluate dose adjustments of GSK1278863 in ND subjects using epoetin beta pegol as control To evaluate dose adjustments of GSK1278863 in PD subjects 	
 Distribution of the dose level Duration of treatment interruption due to Hgb >13 g/dL Frequency of dose adjustments

 To evaluate the overall Hgb control by GSK1278863 in ND subjects using epoetin beta pegol as control To evaluate the overall Hgb control by GSK1278863 in PD subjects 	
 Hgb at each assessment time point and change in Hgb from baseline to each assessment time point Number (%) of subjects with Hgb within the target range (11.0-13.0 g/dL) at each assessment time point Proportion (%) of time with Hgb within the target range (11.0-13.0 g/dL) in the primary efficacy evaluation period (Weeks 40 to 52) Time (number of days) to the lower Hgb target (11.0 g/dL) Number (%) of subjects who have an Hgb level of less than 7.5 g/dL Number (%) of subjects who have an Hgb increase of more than 2 g/dL over any 4 weeks before Week 52 Number (%) of subjects who achieve an Hgb level of more than 13.0 g/dL and number of episodes

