
 Following definition will be based on “assumed” treatment stop date because the treatment stop date is not captured in eCRF. 
Definition:
 
 If a subject has completed the treatment period (i.e., Week 52 visit record is present), treatment stop date will be calculated as Week 52 visit date.. 
 Week 52 visit date will be based on laboratory Hgb date. HemoCue Hgb date will be used when laboratory Hgb date is unavailable. If a subject has withdrawn from the treatment period (i.e., Week 52 visit record is missing), treatment stop date will be calculated as the latest dosing start date + XX days (1 day before the next treatment start date if a subject hadn’t withdrawn) 
 Subjects will have every 2 weeks or every 4 weeks injection of epoetin beta pegol, therefore assumed treatment stop date could include “+ 13 or 27 days” to mimic every 2 weeks or every 4 weeks dosing.

Subgroup definition
 
 For general considerations, see Section 5.4.2 Regarding prior ESA type, prior ESA dose, and ERI, see Section 15.6.2 Baseline iron use = use or non-use of pre-therapy iron medications (including ferric citrate (trade name Riona), see Section 15.6.3). History of diabetes will be derived from the current history diabetes (Yes/No) in medical history records. CKD stage will be derived from the eGFR measurement at a screening visit Cohort will be derived from the randomization number. 
 Cohort 1 = Randomization Number in PPD Cohort 2 = Randomization Number in PPD Cohort 3 = Randomization Number in PPD Dialysis will be derived from the randomization number. 
 ND subjects = Cohort 1 or 3 PD subjects = Cohort 2

Time Definitions (per GSK standard principles)
 
 1 week = 7 days 1 month = 30.4375 days 1 year = 365.25 days

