Period for Compliance Calculation	Dosing Start Date	Dosing Stop Date ^[2]
0 – 2 Week ^[1]	Treatment Start Date	Day 1 Dosing Stop Date
0 – 4 Week (Cohort 1)	Treatment Start Date	Day 1 Dosing Stop Date
0 – 4 Week (Cohort 3)	Treatment Start Date Week 2 Dosing Start Date	Day 1 Dosing Stop Date Week 2 Dosing Stop Date
2 – 4 Week ^[1]	Week 2 Dosing Start Date	Week 2 Dosing Stop Date
Primary Efficacy Evaluation Period (40 – 52 Week)	Dosing Start Date at each visit from Week 40 to 48	Dosing Stop Date at each visit from Week 40 to 48
Overall	Dosing Start Date at each visit	Dosing Stop Date at each visit

[1] Compliance will not be calculated for Cohort 1.
 
[2] If Dosing Stop Date is missing Treatment Stop Date will be used.
		
Treatment Compliance of Epoetin Beta Pegol		

 ● Treatment compliance of epoetin beta pegol will be based on dosing records (dose per every 2 or 4weeks are captured) and categorized as Under compliance, Compliant, and Over Compliant 
 ○ Calculated compliance < 80% → Under Compliant ○ Calculated compliance ≥ 80% and ≤ 120% → Compliant ○ Calculated compliance > 120% → Over Compliant ● Calculated compliance will be provided to derive compliance category only, not provided for any displays. It will be carried using the following formula: 
 ○ Calculated Compliance (%) = [(Total # of dosing) / (Total # of planned dosing)] x 100 ○ Total # of dosing = Sum of Numbers of dosing records where Prescribed Dose equals Actual Dose ○ Total # of planned dosing = Sum of # of planned dosing of each dosing records ○ # of planned dosing = Duration / 14 (if Frequency = every 2 weeks and Prescribed dose ≠ 0) Duration / 28 (if Frequency = every 4 weeks or Prescribed dose = 0) ○ Duration = Start Date of next dosing record – Start Date 
 ▪ If next dosing record is missing, Treatment Stop Date (see Section 15.6.1)+ 1 day will be 		

Exposure	
used. instead of Start Date of next dosing record.	

 Dosing records included in compliance calculation for each period are as below. 	
Period for Compliance Calculation	Dosing Records
0 – 2 Week ^[1]	First record of Day 1
0 – 4 Week	Day 1 to Week 2 (Day 1 for ESA users in Cohort 1)
2 – 4 Week ^[1]	Day 1 (ESA users) Week 2 (ESA non-users)
Primary Efficacy Evaluation Period (40 – 52 Week)	Week 40 to 48
Overall	All records

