
 • Time to reach the lower Hgb target will be determined as follows: 
 ○ Time to reach the lower Hgb target = Date to reach the lower Hgb target – Randomization Date + 1 day • Subjects who could not reach the lower Hgb target during on-therapy will be regarded as censored. Censored time will be determined as follows: 
 ○ Censored time = Treatment Stop Date – Randomization Date + 1
Dose Adjustment
Dose adjustment algorithm

 • Dose Adjustment algorithm will be based on HemoCue Hgb values at scheduled visits. No Hgb values measured at unscheduled visits will be included. • Dose will be derived from actual dose. • The following table illustrates the algorithm using analysis flags as below: 
 ○ (FL_A): Adjustment flags will be counted if actual dose is changed from that of the previous visit.

Dose Adjustment

- (FL_B): Over 13 g/dL flags will be counted if HemoCue Hgb >13 g/dL is observed.
 - (FL_C): Interruption flags will be counted if actual dose is zero.
- Treatment durations in each visit will be calculated based on the following formula:
- Daprodustat
Duration (days) = Treatment Stop Date in the visit – Treatment Start Date in the visit + 1 day
 - Epoetin beta pegol group
Treatment stop date in the visit will be derived from [treatment start date in the next visit – 1 day]. If there is no record of the next scheduled visit, Treatment Stop Date (see Section 15.6.1) will be applied for the record.

Illustration of dose adjustment algorithm (24-week case)

Visit (Example)	Treatment Start date/ Stop date	Duration	HemoCue Hgb (g/dL)	Dose (mg)	(FL_A)	(FL_B)	(FL_C)
					Adjust-ment	Over 13 g/dL	Inter-ruption
Day 1	PPD	29	11.1	4	N	N	N
Week 4		14	11.4	4	N	N	N
Week 8		30	11.8	2	Y	N	N
Week 12		31	13.4	0	Y	Y	Y
Week 16		30	12.6	0	N	N	Y
Week 20		31	11.7	1	Y	N	N
Week 24	-	-	12.3	-	-	N	-

For programmers, note that the flags are for the purposed of illustration, and are not intended to imply any type of requirement.

- For summary tables, further details are described within the next items;
- 'Duration (days) of treatment interruption due to Hgb >13 g/dL'
 - 'Dose adjustment'
 - Number of dose adjustment to reach the lower Hgb target (11.0 g/dL)

Duration (days) of treatment interruption due to Hgb >13.0 g/dL

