Calculation of duration of treatment interruption due to Hgb >13.0 g/dL will be based on the dose adjustment algorithm specified in the protocol.

- Duration (days) = Sum of [Duration]_n
where
[Duration]_n represents exposure duration at visit n to meet the following.
 - Treatment interruption is made due to HemoCue Hgb over 13 g/dL and consecutive until treatment is resumed.

In the above illustration, duration = 61 (days), from Week 12 and 16 visit records.

Dose adjustment

Calculation of frequency of dose adjustment will be based on the above algorithm.

- Number of dose adjustment will be counted for each subject as follows:
 - Counts of adjustment flag = 'Y'

Dose Adjustment
Number of dose adjustment to reach the lower Hgb target (11.0 g/dL)

 Reaching the lower Hgb target will be determined on the basis of central laboratory Hgb. Subjects who has a baseline central laboratory Hgb value within target range or who does not reach the lower Hgb target during treatment period will be excluded from the summary. Number of dose adjustment to reach the lower Hgb target will be counted for each subject as follows 
 Counts of adjustment flag = 'Y' at visits before Date to reach the lower Hgb target.

Iron Endpoints									
Oral Iron Use									

 The following iron-containing drugs will not be included in the analysis of iron use. 
 GSK drug code: 54909401 (SUCROFERRIC OXYHYDROXIDE; P-TOL). 									
Subjects who used IV and/or oral iron									

 Number of subjects who used IV and/or oral iron will be summarized Subjects who used IV and/or oral iron will be defined as follows: 
 Subjects with on-therapy IV and/or oral iron medication collected in a specific eCRF form (CONMEDS-IRON). Regarding oral iron use, the number of subjects who used ferric citrate and other than ferric citrate will also be counted respectively. 									
Oral Iron Dose by Quarter									

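### As written, Section 15.6.3 runs an epoetin beta pegol interruption record to the end of treatment whenever the next scheduled visit has no record, even if dosing resumes later

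*SAP*

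**What the plan says.** Section 2.2 lists "Duration of treatment interruption due to Hgb >13 g/dL" among the other secondary endpoints for evaluating dose adjustments, with epoetin beta pegol as control in non-dialysis subjects. Section 15.6.3 (Dose Adjustment) builds it from the durations of visit records.

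- **Daprodustat:** "Duration (days) = Treatment Stop Date in the visit – Treatment Start Date in the visit + 1 day".
- **Epoetin beta pegol, usual case:** "Treatment stop date in the visit will be derived from [treatment start date in the next visit – 1 day".
- **Epoetin beta pegol, fallback:** "If there is no record of the next scheduled visit, Treatment Stop Date (see Section 15.6.1) will be applied for the record".
- **Records that count towards the endpoint:** "Treatment interruption is made due to HemoCue Hgb over 13 g/dL and consecutive until treatment is resumed".

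Section 15.6.1 defines the epoetin stop date that the fallback uses. If the Week 52 visit record is present, "treatment stop date will be calculated as Week 52 visit date". For a subject who withdrew, it is the last dosing start plus an allowance: "assumed treatment stop date could include “+ 13 or 27 days” to mimic every 2 weeks or every 4 weeks dosing".

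For epoetin compliance, Section 15.6.2 measures the same kind of interval differently: "Duration = Start Date of next dosing record" minus the record's own start date. Treatment Stop Date plus 1 day replaces the next start only when there is no next dosing record.

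**The concern.** The fallback is sensible for a subject's last record. Its trigger is wider than that: it applies whenever the very next scheduled visit is empty, and nothing in the text asks whether the subject was dosed later. A single missed visit during an interruption would then have all the remaining treatment time counted as interruption, including time after dosing restarted. A second 0 µg record after the gap would be added on top, so the same days would be counted twice.

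The formula for daprodustat closes each record with a stop date from the same visit and has no fallback. Any error from this sentence therefore falls on one arm of a summary shown by treatment group. Under Section 7.3.2 the duration is summarised only over subjects who had such an interruption, so the denominator may be small and one long value can move the mean and set the maximum.

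**Working it through.** **The plan's own figure.** The illustration in Section 15.6.3 gives 61 days, from a Week 12 record of 31 days and a Week 16 record of 30 days: 31 + 30 = 61. This reproduces. The example is in mg and has a record at every visit, so it does not exercise the epoetin fallback.

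**Inputs.** Nominal schedule with visits every 4 weeks, so Week w starts on Day 7w + 1 and Week 52 is Day 365. Completer; 0 µg recorded at Week w because of Hgb above 13 g/dL; no record and no dose at Week w + 4; dosing resumed at Week w + 8.

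**Rule as written.** The record runs to the Week 52 visit:

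365 − (7w + 1) + 1 = 7 × (52 − w) + 1 days.

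**Ended at the next available dosing record.** The last day is the day before Week w + 8:

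(7(w + 8) + 1 − 1) − (7w + 1) + 1 = 56 days, whatever w is.

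| 0 µg record at | As written (days) | Next available record (days) | Excess (days) |
|---|---|---|---|
| Week 4 | 337 | 56 | 281 |
| Week 8 | 309 | 56 | 253 |
| Week 12 | 281 | 56 | 225 |
| Week 16 | 253 | 56 | 197 |
| Week 24 | 197 | 56 | 141 |
| Week 32 | 141 | 56 | 85 |
| Week 40 | 85 | 56 | 29 |

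**Overlap.** Suppose 0 µg at Week 8, no record at Week 12, 0 µg again at Week 16 and resumption at Week 20. The Week 8 record counts 309 days and the Week 16 record 28, so the sum is 337 days. The actual span from Week 8 to Week 20 is 12 × 7 = 84 days.

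**Withdrawn subject.** Take 0 µg at Week 8, Week 12 missed, dosing resumed at Week 16 and the last 4-weekly dose at Week 24. The assumed stop date is Day 169 + 27 = Day 196, so the record counts 196 − 57 + 1 = 140 days against 56. The excess is smaller than for a completer.

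**Effect on the arm mean.** The SAP gives no number of interrupted subjects. Assuming n of them in the epoetin arm and one affected Week 12 record, the mean rises by 225/n: 22.5 days for n = 10, 11.25 for n = 20 and 7.5 for n = 30.

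**Consistency with the rest of the SAP.** In the Week 12 case, 225 of the 281 days fall on or after the restart of dosing, which the endpoint definition excludes. The compliance interval in Section 15.6.2, applied to the same dates, runs from Week 12 to Week 20 and gives 56 days.

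**The case against.** **The sentence may be meant only for a subject's last record.** This is plausible. The compliance rule works that way, and the iron-quarter notes in Section 15.6.3 tie a similar fallback to early withdrawal. But the sentence itself carries no such limit, and a programmer who follows it produces the wrong value.

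**The endpoint definition already stops at resumption.** It does, and it points to about 56 days. That makes it the other half of a contradiction. The definition selects which records to sum, while the fallback sets how long each one is, and nothing says which prevails.

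**The trigger is narrow.** This stands. A 0 µg period is itself a recorded dose state, and HemoCue Hgb and the IWRS call are scheduled at these visits whether or not a dose is given. The case needs a 0 µg record due to high Hgb, an empty next visit and later dosing. The SAP gives no frequency, and nothing in it supports supposing that visits are missed more often during an interruption.

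**A reader might infer that the arm comparison is biased in favour of daprodustat.** The documents do not support that as a result of the trial. The direction of any single error is fixed, but the number of errors may be zero. Section 5.5 speaks in general terms of comparing other secondary endpoints at 5%, yet Sections 7.3.1 and 7.3.2 give this one only descriptive statistics and a listing, with no difference, interval or test. The median and quartiles are also reported and would move little with one outlier. Listing 28 and the subject profiles in Figure 2.36 could expose an odd value.

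**Nor does the SAP show that daprodustat durations are free of error.** Section 15.6.3 has no rule for a missing daprodustat stop date, and the compliance table in Section 15.6.2 allows for that date being missing. What can be said is that the daprodustat formula contains no comparable fallback.

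**Conclusion.** Wrong as written, minor severity. Followed literally, the fallback gives a completer with one missed visit and later resumption 7 × (52 − w) + 1 days of interruption instead of 56: 281 at Week 12, falling to 85 at Week 40. That contradicts both the endpoint definition in the same section and the next-dosing-record rule in Section 15.6.2.

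The figures assume nominal visit days, no dose at the missed visit and dosing at the visit after it; withdrawn subjects are inflated less. The effect is confined to the epoetin side of a descriptive secondary summary (Tables 2.62 and 2.64, Listing 28). Its frequency is unknown, and the primary and principal secondary analyses do not use this duration.

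**What to change.** Replace the fallback sentence, and the sentence before it, in the epoetin part of the dose adjustment algorithm (Section 15.6.3) with:

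*The stop date of a record is the treatment start date of the next available dosing record minus 1 day; Treatment Stop Date is applied only when the subject has no later dosing record.*

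This agrees with the compliance rule in Section 15.6.2 and with stopping the count at resumption. It costs one sentence and one line of programming and needs no new data. If the authors meant the fallback only for the last record, the change states that intent and alters no result.

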The number and percentage of subjects with dose adjustments to reach the lower Hgb target will be provided by treatment group on the basis of on-therapy Hgb. Number of dose adjustment to reach the lower Hgb target will be summarized by treatment group using mean, standard deviation, minimum, median, mode, and maximum. For dose adjustments frequency, the number and percentage of subjects will be provided by the number of dose adjustments (i.e. zero, one, two, three, four, ..., ten, eleven, and twelve or more) by treatment group. For timing of dose adjustments, the number and percentage of subjects with dose adjustments by each assessment visit will be provided by treatment group. Subjects who do not reach the lower Hgb target during treatment period will be excluded from the summary. The summary will also be provided by Prior ESA use.

Number (%) of subjects with each dose at each assessment visit

The number and percentage of subjects with each dose will be provided. Graphical summaries of histogram will be provided with the number of subjects in each dose. Summary and histogram will be produced for each treatment group separately. For daprodustat, dose categories will be classified into 10; N/A (not available), 0 mg (treatment interruption), 1 mg, 2 mg, 4 mg, 6 mg, 8 mg, 12 mg, 18 mg, and 24 mg. For epoetin beta pegol, dose categories will be classified into 9, N/A (not available), 0 µg (treatment interruption), 25 µg, 50 µg, 75 µg, 100 µg, 150 µg, 200 µg, 250 µg. The final visit will be the last visit of treatment exposure for each subject. The summary and histogram will also be provided by Prior ESA use, prior ESA dose, prior ESA type, and ERI.

- **Hgb and Dose**

Profiles over time of Hgb and dose will be plotted for each subject.

- **Iron Use**

Dose of oral iron (mg) during the treatment period and the primary efficacy evaluation period

Monthly Average oral iron dose by quarter (See Section 15.6.3) will be summarized using mean, standard deviation, minimum, P25, median, P75, and maximum. Quarter 1 (Day 1 to Week 12), Quarter 2 (Week 12 to Week 24), Quarter 3 (Week 24 to Week 40), Quarter 4 (Week 40 to Week 52), during the screening period as baseline, and whole treatment period will be used and Quarter 4 represents the primary efficacy evaluation period. This will be also summarized by baseline iron use defined in Section 5.4.2.

Change from baseline in dose of oral iron (mg) during the treatment period and the primary efficacy evaluation period

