Change from baseline in average oral iron dose (See Section 15.6.3) will be summarized using mean, standard deviation, minimum, P25, median, P75, and maximum. Quarter 1 (Day 1 to Week 12), Quarter 2 (Week 12 to Week 24), Quarter 3 (Week 24 to Week 40), Quarter 4 (Week 40 to Week 52), and whole treatment period will be used and Quarter 4 represents the primary efficacy evaluation period. For the ITT population, the treatment differences (daprodustat – epoetin beta pegol) and the associated 95% CIs will also be provided.

Number (%) of subjects who use iron during the treatment period and the primary efficacy evaluation period

The number and percentage of subjects who use iron during the screening period as baseline, the treatment period, and the primary efficacy evaluation period will be summarized separately. These will be also summarized by baseline iron use defined in Section 5.4.2

- **Iron Parameter (ferritin, TSAT, hepcidin, serum iron, and TIBC)**

Based on literature review the distributions of TSAT and hepcidin are skewed and require a log-transformation (See Section 5.2).

Raw observed value at each assessment visits

Ferritin, serum iron, and TIBC values will be summarized by treatment group using mean, standard deviation, 95% CI, minimum, P25, median, P75, and maximum at each assessment visit. TSAT and hepcidin values will be summarized by treatment group using geometric mean, standard error, coefficient of variation, and 95% CI based on log-transformed parameters, median, minimum, and maximum based on original scale at each assessment visit. Graphical summaries will also be provided for each iron parameter. These will be also summarized by baseline iron use, prior ESA use.

Change from baseline at each assessment visit

Change from baseline in ferritin, serum iron, and TIBC values will be summarized by treatment group using mean, standard deviation, 95% CI, minimum, P25, median, P75, and maximum at each assessment visit. Percent Change from baseline in TSAT and hepcidin values (Section 5.2) will be summarized by treatment group using geometric mean, coefficient of variation, and 95% CI based on log-transformed parameters, minimum, median, and maximum based on original scale at each assessment visit.

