15.4.1.3. Study Phases for Concomitant Medication

Treatment State	Definition
Pre-therapy	Concomitant medications that meet either following conditions will be regarded as pre-therapy. 
 • Concomitant Medication Start Date $<$ Randomization Date [a, b, c, j, n] • Concomitant Medication Start Date is missing [g, h, i, m, o] • Randomization Date is missing
On-therapy	Concomitant medications that meet either following conditions will be regarded as on-therapy. 
 • Randomization Date \leq Concomitant Medication Start Date \leq Treatment Stop Date + 1 [d, e, k, p, q, r, s, v] • (Concomitant Medication Start Date $<$ Randomization Date) AND (Randomization Date \leq Concomitant Medication Stop Date) [b, c, n]

Treatment State	Definition
	
 • (Concomitant Medication Start Date < Randomization Date) AND (Concomitant Medication Stop Date is missing) [j] • (Concomitant Medication Start Date is missing) AND (Concomitant Medication Stop Date ≥ Randomization Date) [h, i, o] • (Concomitant Medication Start Date is missing) AND (Concomitant Medication Stop Date is missing) [m]
Post-therapy	
Concomitant medications that meet either following conditions will be regarded as post-therapy.
 
 • Concomitant Medication Stop Date > Treatment Stop Date [c, e, f, l, r, t, v] • Concomitant Medication Stop Date is missing [j, k, l, m, s, u]

NOTES:

- Data of concomitant medication includes anti-hypertensive medication, ESA, iron, and blood products and blood supportive care products.
- Alphabets in brackets after the conditions correspond to each case in following illustrations.

Illustrations of the pre-therapy, on-therapy, and post-therapy for concomitant medications are included below:

	Pre-therapy	On-therapy		Post-therapy		Pre-therapy medication	On-therapy medication	Post-therapy medication
(a)	x—x					Y	N	N
(b)	x—		—x			Y	Y	N
(c)	x—		—			Y	Y	Y
(d)			x—x			N	Y	N
(e)			x—			N	Y	Y
(f)						N	N	Y
(g)	?—x					Y	N	N
(h)	?—		—x			Y*	Y	N
(i)	?—		—			Y*	Y*	Y
(j)	x—		—			Y	Y**	Y**
(k)			x—			N	Y	Y**
(l)						N	N	Y
(m)	?—		—			Y***	Y***	Y***
(n)	x—	x				Y	Y	N
(o)	?—	x				Y*	Y	N
(p)		x	—x			N	Y	N
(q)		x	—			N	Y	N
(r)				x		N	Y	Y
(s)				x		N	Y	Y**
(t)					x	N	N	Y
(u)					x	N	N	Y
(v)			x—		x	N	Y	Y

x = start/stop date of medication
 ? = missing start/stop date of medication

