
 Records of on-therapy iron medication will be used for the following calculations. Summary will be created for all subjects (both iron users and iron non-users) and iron users respectively. In a summary containing all subjects, iron dose of subjects who do not use iron medication will be calculated as 0 mg. Monthly average oral iron during the treatment period = Total oral iron dose (mg) during the treatment period / (duration in the treatment period (days) / 30.4375 days) Monthly average oral iron by quarter = Total oral iron dose during each quarter (mg) / (duration in a quarter (days) / 30.4375 days). Total oral iron dose during each quarter (mg) will be carried with the following formula using each record. Duration will be derived from iron medication start/stop date: 
 Total oral iron dose during each quarter (mg) = (iron dose₁*frequency₁*duration₁) + ... + (iron dose_n*frequency_n*duration_n) Duration (days) = (stop date₁ - start date₁ + 1) + ... + (stop date_n - start date_n + 1) Frequency is defined as follows: 
 If subject receives iron dose with once daily → frequency = 1 If subject receives iron dose with BID → frequency = 2 If subject receives iron dose with TID → frequency = 3 If subject receives iron dose with QID → frequency = 4 
Total oral iron dose (mg) during the treatment period will be carried in the same manner.
 
 Quarters/Duration will be defined as follows: 
  
 	Start Date	End Date	
   
 baseline	Screening Date	Randomization Date - 1	
 
 Treatment	Randomization Date	Treatment Stop Date	
  
		Start Date	End Date	baseline	Screening Date	Randomization Date - 1	Treatment	Randomization Date	Treatment Stop Date
	Start Date	End Date							
baseline	Screening Date	Randomization Date - 1							
Treatment	Randomization Date	Treatment Stop Date							

period		
Quarter 1	Randomization Date	Treatment Start Date at Week 12 - 1 day
Quarter 2	Treatment Start Date at Week 12	Treatment Start Date at Week 24 - 1 day
Quarter 3	Treatment Start Date at Week 24	Treatment Start Date at Week 40 - 1 day
Quarter 4 ^[1]	Treatment Start Date at Week 40	Treatment Stop Date

NOTES:

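### The baseline oral iron dose omits iron records that ended before randomization, because the calculation is limited to on-therapy records

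*SAP*

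**What the plan says.** All references are to the SAP.

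- **Record filter.** Section 15.6.3, Oral Iron Dose by Quarter, begins: "Records of on-therapy iron medication will be used for the following calculations". In the all-subjects summary, "iron dose of subjects who do not use iron medication will be calculated as 0 mg".
- **Baseline window.** The period table in the same block starts baseline at the screening date and ends it at "Randomization Date - 1", so the window lies wholly before randomization.
- **Meaning of on-therapy.** Section 15.4.1.3 defines the term in a list introduced by "Concomitant medications that meet either following conditions will be regarded as on-therapy". A note there confirms that iron is covered: "Data of concomitant medication includes anti-hypertensive medication, ESA, iron, and blood products and blood supportive care products". Medication that stopped before randomization, with a known start (case a) or a missing start (case g), is pre-therapy only.
- **Where the baseline is used.** Section 7.3.2 plans a dose summary with iron "during the screening period as baseline, and whole treatment period will be used". It also says "Change from baseline in average oral iron dose (See Section 15.6.3) will be summarized", with treatment differences and 95% CIs in the ITT population.
- **Subgroup.** Section 15.6.1 uses a different set of records: "Baseline iron use = use or non-use of pre-therapy iron medications".

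**The concern.** The filter and the baseline window work against each other. The window contains only pre-randomization days, but a record enters only if it reaches randomization or starts later. Iron taken and ended inside the window is what a screening-period baseline should capture, and it is removed. I found no sentence exempting the baseline row.

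This defeats the stated purpose. Section 16 records that Amendment 1 added the baseline summary because some subjects use oral iron at screening and the value helps in judging change. A programmer must either follow the text and produce wrong baselines, or depart from it without a written rule. The same filter reaches the planned number (%) of iron users at baseline, because Section 15.6.3 also defines iron users by on-therapy records.

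**Working it through.** The plan gives no figure on this point to reproduce, so the check applies its rules to example subjects.

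**Inputs from the SAP.** On-therapy rule (15.4.1.3); replacement of start and stop dates, and splitting of records at period boundaries (15.6.3); month of 30.4375 days (15.6.1); 4-week screening, taken as 28 days (2.3).

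**Assumed for illustration.** 100 mg once daily unless stated, and treatment to Day 364.

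**Formula (15.6.3).** Monthly average = total mg in period / (days in period / 30.4375). Change = Quarter 4 minus baseline.

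**Example subjects (mg/month)**

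| Subject | Baseline as written | Baseline, all records | Quarter 4 | Change as written | Change, all records |
|---|---|---|---|---|---|
| A: stops the day before randomization | 0 | 3043.75 | 0 | 0 | -3043.75 |
| B: stops on the randomization date | 3043.75 | 3043.75 | 0 | -3043.75 | -3043.75 |
| C: continues throughout | 3043.75 | 3043.75 | 3043.75 | 0 | 0 |
| D: 100 mg for 14 days, then a new ongoing 50 mg record | 760.94 | 2282.81 | 1521.88 | +760.94 | -760.94 |
| E: stops 8 days before randomization, restarts at Week 40 | 0 | 2282.81 | 3043.75 | +3043.75 | +760.94 |

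Arithmetic for A: 28 x 100 / (28 / 30.4375) = 3043.75.

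Arithmetic for D: all records give (14 x 100 + 14 x 50) / (28 / 30.4375) = 2282.81. As written, only the 50 mg record survives: 14 x 50 / (28 / 30.4375) = 760.94.

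Arithmetic for E: 21 days of iron in screening give 21 x 100 / (28 / 30.4375) = 2282.81.

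A and B differ by one day in stop date, yet the baseline moves from zero to the full dose. B and C show that records reaching randomization are handled properly: the splitting rule carries their screening part into baseline. D shows a reduction reported as an increase.

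**Effect on the mean.** If a share p of subjects take m mg/day through the whole window and stop just before randomization with no other iron record, mean baseline is understated by p x m x 30.4375. If their stop dates are spread evenly over the window, average exposure is about half, and so is the error. Both p and m are assumed.

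| p, m | Upper bound (mg/month) | Stops spread evenly (mg/month) |
|---|---|---|
| 2%, 50 mg/day | 30 | about 15 |
| 5%, 100 mg/day | 152 | about 76 |
| 10%, 200 mg/day | 609 | about 304 |

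**The case against.** The strongest reply is that little of importance depends on this row. The oral iron endpoints in Section 2.2 are doses in the study period and in Weeks 40-52, and the number using oral iron in Weeks 40-52. The on-therapy filter is right for those periods. Change from baseline is an added display, and Section 5.5 treats the other secondary endpoints as complementary or exploratory without multiplicity adjustment. The intent is also clear from Section 7.3.2, so the lead sentence may simply be too broad. All of this stands and limits the weight of the point. It does not make the sentence correct, because the text followed literally gives the wrong baseline.

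A reader might infer three stronger things that the SAP does not support:

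- **That every reduction begun in screening is lost.** Records that reach randomization (B and C) contribute in full, and a replacement record that continues (D) contributes its part. Only closed records are dropped.
- **That the treatment comparison is biased.** The dropped records precede randomization, so the omission should be balanced between arms in expectation. Chance imbalance and precision remain affected.
- **That the filter alone explains baseline iron users with a 0 mg baseline.** The subgroup counts any pre-therapy iron, including IV iron, with no lower limit at the screening date. Subjects on IV iron only, or whose oral iron ended before screening, would have a 0 mg oral baseline under any rule.

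**Conclusion.** The rule is wrong as written, within a narrow scope. Iron records that ended before randomization are left out of the baseline oral iron dose. The value becomes 0 mg in the all-subjects summary when no other iron record covers screening, and is understated when another record does. In the iron-users summary such a subject may be absent altogether, since users are defined by on-therapy iron.

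What suffers is the baseline row, individual and within-arm change from baseline, and the precision of the treatment difference in change. Treatment-period and Weeks 40-52 doses are unaffected, as are the primary and principal secondary analyses.

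The size cannot be fixed from the SAP, because the number of subjects stopping or switching iron during screening is not given. The 152 mg/month figure for 5% of subjects at 100 mg/day is a ceiling that presumes iron throughout screening, not an estimate. The point merits correction because the error is certain for any affected subject and simple to remove.

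**What to change.** In Section 15.6.3, limit the on-therapy filter to the treatment period and Quarters 1-4. For the baseline row, state that all oral iron records, pre-therapy or on-therapy, that overlap the screening date to the day before randomization are used, truncated to that window. Apply the same record rule to the baseline number (%) of iron users.

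The cost is a sentence or two of SAP text and a small programming change. The plan already identifies pre-therapy iron for its subgroup, so no new data are needed.

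The change reduces the mismatch with the baseline iron use subgroup but does not remove it. A footnote to the by-subgroup dose tables (2.84 and 2.85) could say that the subgroup also includes IV iron and iron that ended before screening.
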